6.7 Treatment of Overdose

For this study, an overdose is any dose of study intervention given to a participant that exceeds the maximum study dose for a single vaccination.

GSK does not recommend specific treatment for an overdose.

In the event of an overdose, the investigator should:

- Contact the medical monitor immediately.
- Evaluate the participant to determine, in consultation with the medical monitor, whether study intervention should be interrupted or whether the subsequent dose should be reduced.

6.8 Concomitant Therapy

Any medication or vaccine (including over-the-counter or prescription medicines, recreational drugs, vitamins, and/or herbal supplements) or other specific categories of interest that the participant is receiving at the time of enrollment or receives during the study must be recorded along with:

- Reason for use
- Dates of administration including start and end dates
- Dosage information including dose and frequency
- Route of administration
- For vaccines (if applicable) include brand name and manufacturer (plus lot number if available)

Concomitant therapy that meets the exclusionary criteria for this study is listed in Section [5.2.2](#).

The medical monitor should be contacted if there are any questions regarding concomitant or prior therapy.

7.0 DISCONTINUATION OF STUDY INTERVENTION AND PARTICIPANT DISCONTINUATION/WITHDRAWAL

Discontinuation of specific study sites or of the study as a whole are detailed in Section 10.1.11.

7.1 Discontinuation of Study Intervention

Discontinuation of study intervention refers to any participant who has received the first dose and has not received the second dose of study intervention. A participant who discontinued study intervention may continue other study procedures (e.g., safety assessment or immunogenicity testing), planned in the study protocol at the discretion of the investigator.

The primary reason for premature discontinuation of the study intervention will be documented on the eCRF as follows:

- AE requiring expedited reporting (i.e., SAE, potential immune-mediated disease [pIMD])
- Unsolicited non-serious AE
- Safety laboratory assessment results that are Grade 2 (moderate) or greater based on FDA toxicity grading that did not resolve, after repeat testing, to FDA toxicity Grade 1 or less (Figure 2)
- Solicited event
- Protocol Deviation
- Not willing to be vaccinated
- Pregnancy
- Inappropriate enrollment
- Other (specify)

It may be necessary for a participant to permanently discontinue study intervention. If study intervention is permanently discontinued, the participant will be encouraged to remain in the study to be evaluated for post- dose visits and for safety follow-up. See the Schedule of Activities (SoA) in Section 1.3 for data to be collected at the time of discontinuation of study intervention and follow-up and for any further evaluations that need to be completed.

Participants who discontinue study intervention will not be replaced.

7.1.1 Contraindications to Subsequent Study Intervention(s) Administration

The eligibility for subsequent study intervention administration must be confirmed before administering any additional dose.

Participants who meet any of the criteria listed below or criteria listed in Sections 5.2.1 and 5.2.2 should not receive additional doses of study intervention. Such participants should be encouraged to continue other study procedures. All relevant criteria for discontinuation of study intervention administration must be recorded in the eCRF.

- Participants who experience any SAE judged to be possibly or probably related to study intervention or non-study concomitant vaccine/product, including hypersensitivity reactions.
- Participants who develop any new condition which, in the opinion of the investigator, may pose additional risk to the participants if they continue to participate in the study.
- Anaphylaxis following the administration of study interventions.
- Any condition that in the judgment of the investigator would make intramuscular injection unsafe.
- Occurrence of a new pIMD that, in the opinion of the investigator, exposes the participant to unacceptable risk from subsequent vaccination. In such cases, the investigator should use their clinical judgment prior to administering the next dose of the study interventions. Refer to Section 8.5.7.1 for the definition of pIMD.
- Pregnancy.

7.2 Participant Discontinuation/Withdrawal from the Study

A participant may withdraw from the study at any time at his/her own request for any reason (or without providing any reason) or may be withdrawn at any time at the discretion of the investigator for safety, behavioral, or compliance reasons.

Participants who discontinue study intervention or withdrawn from the study due to a safety issue are required to have a follow-up visit to monitor the status of the safety issue. Otherwise, the participant will be permanently discontinued from the study intervention and the study at that time.

All data and samples collected up to and including the date of withdrawal of/last contact with the participant will be included in the study analyses. If the participant withdraws consent for disclosure of future information, the Sponsor may retain and continue to use any data collected before such a withdrawal of consent.

If a participant withdraws from the study, the participant may request destruction of any samples taken and not tested, and the investigator must document this in the site study records.

The primary reason for study withdrawal will be documented in the eCRF based on the list below:

- AE requiring expedited reporting (i.e., SAE, pIMD)

- Unsolicited non-serious AE
- Solicited events
- Protocol deviation
- Withdrawal by participant, not due to an AE*
- Migrated/Moved from the study area
- Lost to follow-up
- Sponsor study termination
- Inappropriate enrollment
- Other (specify)

*If a participant is withdrawn from the study because he/she has withdrawn consent and provided the reason for its withdrawal, the investigator must document this reason in the eCRF.

Participants who are withdrawn from the study because of SAEs/AEs must be clearly distinguished from participants who are withdrawn for other reasons. Investigators will follow participants who are withdrawn from the study as result of an SAE/AE until the event is resolved (see Section 10.5.3).

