7.3 Lost to Follow-up

A participant will be considered lost to follow-up if he/she repeatedly fails to return for scheduled visits and is unable to be contacted by the study site.

The following actions must be taken if a participant fails to return to the clinic for a required study visit:

- The study site must attempt to contact the participant and reschedule the missed visit as soon as possible, counsel the participant on the importance of maintaining the assigned visit schedule and ascertain whether the participant wishes to and/or should continue in the study.
- Before a participant is deemed lost to follow-up, the investigator or designee must make every effort to regain contact with the participant (where possible, 3 telephone calls, and if necessary, a certified letter to the participant's last known mailing address or local equivalent methods). These contact attempts should be documented in the participant's medical record.
- Should the participant continue to be unreachable, he/she will be considered to have withdrawn from the study.

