8.5.1 Time Period and Frequency for Collecting AE, SAE, pIMD, MAE Information

Serious AEs assessed as related to study participation (e.g., study intervention, protocol-mandated procedures, invasive tests, or change in existing therapy) or related to a

GSK product (non-IMP) will be recorded from the time a participant consents to participate in the study.

All SAEs (not related to study participation), pIMDs, medically attended adverse events (MAEs), and pregnancies will be collected from the start of study intervention until 6 months after the last vaccination at the time points specified in the SoA (Section 1.3).

Medical occurrences that begin before the start of study intervention but after obtaining informed consent will be recorded as medical history/current medical conditions, not as AEs.

All SAEs and pIMDs (pIMDs can be serious or non-serious) will be recorded and reported to the Sponsor or designee immediately and under no circumstance should this exceed 24 hours of the investigator's awareness of the event, as indicated in Section 10.5.5. The investigator will submit any updated SAE or pIMD data to the Sponsor or designee within 24 hours of their awareness of the updated information.

All unsolicited AEs that occur within 21 days following administration of each dose of study intervention and MAEs that occur at any time during the study must be recorded onto the appropriate section of the eCRF, irrespective of their intensity or whether or not they are considered related to the study intervention.

All solicited events that occur within 7 days following administration of each dose of study intervention must be recorded into the diary, irrespective of intensity. All other AEs occurring within this time frame should be recorded on the appropriate section of the eCRF, irrespective of their intensity or whether or not they are considered related to the study intervention.

Investigators are not obligated to actively seek information on AEs or SAEs after conclusion of the study participation. However, if the investigator learns of any SAE, including a death, at any time after a participant has been discharged from the study, and he/she considers the event/cause of death to be reasonably related to the study intervention or study participation, the investigator must promptly notify the Sponsor or designee.

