8.5.6 Pregnancy

Details of all pregnancies in study participants will be collected after the start of study intervention and until the outcome of the pregnancy is known. Female participants who become pregnant after the first study intervention dose must not receive the second dose of the study intervention but may continue other study procedures at the discretion of the investigator.

If a pregnancy is reported, the investigator will record pregnancy information on the appropriate form and submit it to the Sponsor or designee within 24 hours of learning of the participant's pregnancy and should follow the procedures outlined in Section [10.5.3](#)

While pregnancy itself is not considered to be an AE or SAE, any pregnancy complication or elective termination of a pregnancy for medical reasons will be reported as an AE or SAE.

If the outcome of the pregnancy meets the criteria for immediate classification as an SAE (i.e., spontaneous abortion, stillbirth, neonatal death, or congenital anomaly [including if found in an aborted fetus, stillbirth, or neonatal death]) the investigator will report according to the SAE reporting procedures described in Section [10.5.5](#).

The participant will be followed to determine the outcome of the pregnancy. The investigator will collect follow-up information on the participant and the neonate and the information will be forwarded to the Sponsor or designee.

Any post-study pregnancy-related SAE considered reasonably related to the study intervention by the investigator will be reported to the Sponsor as described in Section [8.5.5](#). While the investigator is not obligated to actively seek this information in former study participants, he or she may learn of an SAE through spontaneous reporting.

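### Protocol 7.2's 'Otherwise' sentence, read literally, takes participants who stop vaccination for a non-safety reason off study, contrary to 7.1, 7.1.1, 8.5.6 and 10.6.2 (minor wording correction)

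*Protocol*

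**What the plan says.** Protocol 7.2 opens its rule with "Participants who discontinue study intervention or withdrawn from the study due to a safety issue are required to have a follow-up visit", for monitoring of the safety issue. The next sentence reads "Otherwise, the participant will be permanently discontinued from the study intervention and the study at that time".

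Four other places deal with participants who have had dose 1 and will not have dose 2:

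- Protocol 7.1 defines this group. Its list of reasons includes "Not willing to be vaccinated", pregnancy, protocol deviation and inappropriate enrollment. On permanent discontinuation of the intervention it says that "the participant will be encouraged to remain in the study" for post-dose visits and safety follow-up, whatever the reason.
- Protocol 7.1.1 bars dose 2 on several grounds, among them pregnancy and the criteria in 5.2.1 and 5.2.2, and adds: "Such participants should be encouraged to continue other study procedures".
- Protocol 8.5.6 says that a participant who becomes pregnant after dose 1 gets no second dose but "may continue other study procedures at the discretion of the investigator".
- Protocol 10.6.2 repeats the pregnancy rule.

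On data collection, Protocol 8.5.1 says that SAEs, pIMDs, MAEs and pregnancies "will be collected from the start of study intervention until 6 months after the last vaccination". SAP 2.4 makes SAE, pIMD and MAE occurrence through 6 months primary safety variables on the Exposed Set, without imputation of missing data. SAP 5.4 places everyone who received a study intervention in that set.

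**The concern.** The sentence before 'Otherwise' expressly includes people who only stop the intervention. Its literal complement therefore includes people who only stop the intervention for a reason unrelated to safety. For them 7.2 prescribes removal from the study, while 7.1 prescribes encouragement to stay. The wording in 7.2 is mandatory. The retention wording elsewhere is softer: participants are encouraged to stay, or may continue at the investigator's discretion. Protocol 8.0 allows no waivers and requires adherence, so a site could follow 7.2 in good faith.

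What is at stake is active safety follow-up after one dose of an adjuvanted vaccine. A participant removed at the dose 2 visit stays in the Exposed Set denominator. With no imputation, later events that nobody collects are counted as no event, so the 6-month percentages can only be pushed down.

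**Working it through.** **Reading the sections side by side.** The plan gives no figure on this point, so the check is mainly textual.

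1. *Who falls under 'Otherwise'?* The preceding sentence names two groups, those who stop the intervention and those withdrawn from the study, each because of a safety issue. Stopping the intervention for a non-safety reason is outside it and so falls under 'Otherwise'.
2. *Which 7.1 and 7.1.1 grounds are non-safety?* From 7.1: unwillingness, protocol deviation, inappropriate enrollment and pregnancy. From 7.1.1: mainly pregnancy and the 5.2.2 therapy criteria. Related SAE, anaphylaxis, a new pIMD and a new risk condition are safety issues and go to the follow-up-visit branch, so the clash with 7.1.1 is partial. Pregnancy can fall under 'Otherwise' because 8.5.6 states that it is not itself an AE or SAE.
3. *What is lost on removal?* Scheduled collection of SAEs, pIMDs and MAEs. At the planned dose 2 visit (21 days after dose 1), 180 − 21 = 159 days remain if 6 months run from dose 1. If Visit 6 is counted from the planned dose 2 date, 180 days remain.
4. *What is kept?* Under 8.5.1 the investigator must still report any SAE learned of after discharge and considered reasonably related. Under 8.5.6 pregnancies are followed to outcome.
5. *What is untouched?* The Per Protocol Set requires both doses, so these participants are outside the primary seroprotection analysis whether or not they stay.

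**Illustrative size.** The stopping rate, the share of stoppers removed because of 7.2, and the true event rate are not in the documents. Assume that 2–10% stop for non-safety reasons at the planned dose 2 visit, that 25–100% of those are removed, and that the event rate is constant over time. Let *f* = stopping rate × share removed, *p* = true 6-month percentage, and *T* = 180 or 201 days (201 = 21 + 180). Then

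reported percentage = (1 − *f*)·*p* + *f*·[1 − (1 − *p*)^(21/*T*)].

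For *p* = 20%, *T* = 180, *f* = 10%: 1 − 0.8^(21/180) = 0.0257, so 0.9 × 0.20 + 0.1 × 0.0257 = 18.26%.

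| Stop × removed | *f* | Removed of 520 | Reported if true 20% | Reported if true 5% |
|---|---|---|---|---|
| 2% × 25% | 0.5% | 2.6 | 19.91% | 4.98% |
| 2% × 100% | 2% | 10.4 | 19.65% | 4.91% |
| 10% × 25% | 2.5% | 13 | 19.56% | 4.89% |
| 10% × 100% | 10% | 52 | 18.23–18.26% | 4.55–4.56% |

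For scale, 13 events in a subgroup of 65 (20%) has an exact 95% confidence interval of 11.1% to 31.8%. With zero events in 65 the exact upper limit is 1 − 0.025^(1/65) = 5.5%. Removal does not change it, because the denominator does not change.

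**The case against.** The strongest reply is that 7.2 is about leaving the study. Its heading, its opening paragraph, its list of withdrawal reasons and its rule on stored samples all say so. In that setting 'Otherwise' most naturally means that someone leaving without a safety issue needs no further visit. Other text agrees. Section 7.3 has the site "ascertain whether the participant wishes to and/or should continue in the study" after a missed visit. The reasons "Not willing to be vaccinated" and pregnancy appear in the 7.1 list but not in the 7.2 list. SAP 9.1 counts vaccination discontinuation and study discontinuation separately. This stands as evidence of intent, and it is why the point is minor. It does not cure the wording, because the sentence before 'Otherwise' names people who only stop the intervention.

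Two further replies also stand. Retention under 7.1 and 8.5.6 is partly at the investigator's discretion, so some follow-up could be lost without 7.2. And the documents contain nothing to show that any site applied 7.2 literally.

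A reader might infer that the protocol deliberately removes everyone who declines dose 2, or that the 6-month safety percentages are materially understated. Neither is supported. The first is contradicted by 7.1 and by the layout of 7.2. The second needs a stopping rate and a share removed that the documents do not give.

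**Conclusion.** The conflict in the wording is real; the rule is probably unintended. As written, 7.2 ends study participation for someone who stops vaccination for a non-safety reason, and four other sections encourage or allow that person to stay.

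The effect is confined to sites that follow the sentence literally. There, active SAE, pIMD and MAE collection to 6 months would stop, while related SAEs learned of later and pregnancy outcomes would still be reported. The direction of any bias is downward. Its size cannot be determined from the documents and is likely very small. Under the assumptions in the table, the shift with a quarter of stoppers removed is 0.1 to 0.4 points on a true 20%. The extreme row, 10% stopping and all removed, gives 1.7 to 1.8 points, still well inside the sampling error of one age-by-dose subgroup. That row assumes every site follows 7.2 literally, which the likely intent makes improbable, and it takes no account of loss that 7.1 already permits.

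It would be wrong to extend this to the primary immunogenicity conclusion: the Per Protocol Set, the hypotheses and the power do not change. SAP 16 makes the safety summaries descriptive, with no comparison between groups.

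**What to change.** Limit the 'Otherwise' sentence in Protocol 7.2 to participants who withdraw, or are withdrawn, from the study. Add that stopping vaccination alone does not end study participation and that such participants follow 7.1. Possible wording: *A participant who withdraws or is withdrawn from the study for a reason other than safety is discontinued from both the study intervention and the study at that time. A participant who stops study vaccination only remains in the study as described in Section 7.1.*

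The cost is one protocol sentence and a short clarification to sites. No analysis changes and no additional tables are needed: Protocol 9.4.2 and SAP 9.1 already plan counts of vaccination discontinuation and study discontinuation, and disposition listings are planned for the enrolled set.

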7.3 Lost to Follow-up

A participant will be considered lost to follow-up if he/she repeatedly fails to return for scheduled visits and is unable to be contacted by the study site.

The following actions must be taken if a participant fails to return to the clinic for a required study visit:

- The study site must attempt to contact the participant and reschedule the missed visit as soon as possible, counsel the participant on the importance of maintaining the assigned visit schedule and ascertain whether the participant wishes to and/or should continue in the study.
- Before a participant is deemed lost to follow-up, the investigator or designee must make every effort to regain contact with the participant (where possible, 3 telephone calls, and if necessary, a certified letter to the participant's last known mailing address or local equivalent methods). These contact attempts should be documented in the participant's medical record.
- Should the participant continue to be unreachable, he/she will be considered to have withdrawn from the study.

8.0 STUDY ASSESSMENTS AND PROCEDURES

Study procedures and their timing are summarized in the SoA (Section 1.3). Protocol waivers or exemptions are not allowed.

Immediate safety concerns should be discussed with IQVIA immediately upon occurrence or awareness to determine if the participant should continue or discontinue study intervention.

Adherence to the study design requirements, including those specified in the SoA (Section 1.3), is essential and required for study conduct.

All screening evaluations must be completed and reviewed to confirm that potential participants meet all eligibility criteria. The investigator will maintain a screening log to record details of all participants screened and to confirm eligibility or record reasons for screening failure, as applicable.

Procedures and associated data conducted as part of the participant's routine clinical management (e.g., blood count) and obtained before signing of the informed consent form (ICF) may be utilized for screening or baseline purposes provided the procedures met the protocol-specified criteria and were performed within the timeframe defined in the SoA (Section 1.3).

The maximum amount of blood collected from each participant over the duration of the study, including any extra assessments that may be required, will not exceed 240 mL.

Repeat or unscheduled samples may be taken for safety reasons or for technical issues with the samples (e.g., hemolyzed sample). Only one sample per timepoint should be sent to the laboratory for testing.

8.1 Screening Procedures

8.1.1 Informed Consent

The signed informed consent of the participant must be obtained before study participation. Refer to Section 10.1.4 for the requirement on how informed consent will be obtained.

8.1.2 Check Inclusion and Exclusion Criteria

All inclusion and exclusion criteria will be checked as described in Sections 5.1 and 5.2 at Screening Visits and before dosing on Visit 1 and Visit 3.

8.1.3 Collection of Demographic Data

Demographic data according to local regulations such as date of birth, sex, race*, ethnicity*, and occupation will be collected in the eCRF. Collection of sex, race, and ethnicity data is

necessary to assess and monitor the diversity of the trial participants, and to determine if the trial participants are truly representative of the impacted population.

*Differences in the safety and efficacy of certain medical products, including vaccines, have been observed in racially and ethnically distinct subgroups.¹⁸⁻²⁰ These differences may be attributable to intrinsic factors (e.g., genetics, metabolism, elimination), extrinsic factors (e.g., diet, environmental exposure, sociocultural issues), or interactions between these factors. Therefore, both geographic ancestry (race) and ethnicity will be collected for all study participants.

